## **1.3 STUDY RATIONALE AND BENEFIT–RISK ASSESSMENT**

### **1.3.1 Study Rationale**

The current protocol, NP39305, is the first clinical study of RO7020531, designed to assess the safety, tolerability, PK and PD of oral SADs and multiple ascending doses (MAD) administered to healthy male and female volunteers (Part 1); and safety, tolerability, PK and PD effects of treatment with RO7020531 for 6 weeks in CHB patients

(Part 2). Based on the results of this entry-into-human (EIH) study, further development of RO7020531 will include combination studies with other agents to treat CHB.

All SAD and MAD cohorts will be dosed in the fasted state. Dose-escalation will proceed following evaluation of the safety and tolerability of the available data from all previous cohorts.

In the SAD portion of the study, safety and tolerability of ascending doses will be the primary endpoints for dose-escalation. In addition, PK and PD measured by the appearance of select biomarkers indicating activation of a TLR pathway will be evaluated. These biomarkers will be evaluated for each cohort and will be used to decide whether to initiate the MAD portion of Part 1. When PD biomarkers indicating TLR activity are detected within a particular SAD cohort and the dose in that cohort is considered to have adequate safety and tolerability, then that dose may be evaluated in the first MAD cohort, but only if the next higher single dose is also considered safe and well-tolerated. Evidence for TLR-related PD activity will be provided by measuring post-dose changes of selected biomarkers that are known to be activated following stimulation of TLR7 and TLR8. These biomarkers include the protein and metabolite markers IFN- $\alpha$ , IL-12p40, IL-10, IP-10, TNF- $\alpha$ , IL-6, and neopterin and markers of transcriptional responses (ISG15, OAS-1, MX1 and TLR7). The single dose above the dose found to elicit TLR activation will be evaluated in the SAD prior to moving to the MAD. Dose-escalation in the SAD will not proceed if stopping rules are met or if the mean RO7011785 exposure (AUC) reaches the exposure found to be associated with adverse effects in the monkey GLP toxicology studies.

The MAD portion is designed to dose subjects with RO7020531 using a QOD dose regimen that will proceed for two weeks. Previous clinical and non-clinical data with another TLR7 agonist, RO6864018, have shown that the QOD dose schedule provides additional priming of TLR7 response biomarkers and is thought to be a more effective dose regimen mechanistically for HBV treatment. This approach to the HV MAD will therefore allow characterization of safety, PK and PD following QOD dosing. The dose will not be escalated in the HV MAD if stopping rules have been met or if the mean RO7011785 exposure (AUC) reaches the exposure found to be associated with adverse effects in the monkey GLP toxicology studies ( $\sim 2.8 \mu\text{g} \cdot \text{h/mL}$ ).

Part 2 will involve HBeAg-positive and HBeAg-negative virologically suppressed CHB patients, as well as HBeAg-positive patients with CHB who are currently not on antiviral treatment. In Cohorts 1, 2 and 3 of Part 2 of the study RO7020531 will be administered to study patients together with the NUCs they have been taking (tenofovir, entecavir, adefovir, or telbivudine, either as single agents or in combination), which are globally marketed drugs (for the rationale of enrollment of NUC-suppressed patients; see Section 3.2.2.2). Based on preclinical evidence, no drug–drug interaction (DDI) is anticipated with the concomitant NUC treatment. In Cohort 4 of Part 2 of the study RO7020531 will be administered to study patients who are treatment-naïve or not on

treatment for the past 6 months. The primary objective of Part 2 will be the assessment of safety and tolerability of multiple doses of RO7020531 administered for 6 weeks, followed by 6 weeks of follow-up. Based on non-clinical and clinical experience with another TLR7 agonist, RO6864018, safety issues should be apparent within 6 weeks of dosing. This study will allow better understanding of the safety and PD in CHB patients before going on to longer dosing in subsequent studies. The goal of the treatment with RO7020531 in CHB patients is to induce immune cell activation and local cyto/chemokines while limiting AEs related to systemic IFN- $\alpha$ .

### 1.3.2 Benefit-Risk Assessment

No prior clinical experience with RO7020531 exists. The evaluation of potential risks of treatment and specific tests, observations, and precautions required for clinical studies with RO7020531 are based on information from non-clinical toxicology and safety pharmacology studies, and on information from clinical studies with other TLR7 agonists. Safety and tolerability will be carefully assessed, and HVs/patients will be closely monitored. The [RO7020531 IB](#) (Guidance to the Investigator) summarizes potential risks and key risk management activities to consider when dosing this compound.

[REDACTED]

In two Phase I studies with RO7020531, 19 subjects (dosed with 140 mg or higher) developed flu-like symptoms with initial onsets usually after the first, second, or the third dose. *In addition, in Study NP39305 Part 2 Cohort 4, one patient experienced an SAE of flu-like syndrome (see Section 1.2.2).* The flu-like symptoms were mild in the majority of these subjects, [REDACTED]

[REDACTED]

As for all early clinical studies in HVs, there is no direct benefit to the subjects participating in Part 1 of the study. However, this study will be essential in the development of a new treatment for chronic HBV infection, and for selecting the most appropriate dose for a study in HBV-infected patients. It is possible that no long-term benefit to CHB patients may occur in Part 2 of this study; however, data generated in these patients will enable further development of RO7020531 as potentially part of a clinical cure for CHB.

## **2. OBJECTIVES**

### **2.1 PRIMARY OBJECTIVES**

#### **2.1.1 Part 1: SAD and MAD in Healthy Volunteers**

The primary objective is:

- To assess the safety and tolerability of single and multiple ascending doses of RO7020531 administered orally to HVs.

#### **2.1.2 Part 2: Chronic Hepatitis B Patients**

The primary objective is:

- To assess the safety and tolerability of 6 weeks of treatment with RO7020531 administered orally to CHB patients.

### **2.2 SECONDARY OBJECTIVES**

#### **2.2.1 Part 1: SAD and MAD in Healthy Volunteers**

The secondary objectives are:

- To investigate the plasma PK of RO7020531, the main active metabolite RO7011785, and additional metabolites, including RO7018822 and RO7033805, following single and multiple ascending oral doses of RO7020531.
- To investigate the urine PK of RO7020531, the main active metabolite RO7011785, and additional metabolites, including RO7018822 and RO7033805, in pooled urine samples of healthy subjects after single ascending oral doses of RO7020531.
- To investigate the effect of RO7020531 on PD parameters following single ascending doses and multiple ascending doses administered QOD.
- To evaluate the effect of RO7020531 dosing on electrocardiogram (ECG) parameters after single and multiple ascending oral doses using exposure-response analysis.

#### **2.2.2 Part 2: Chronic Hepatitis B Patients**

The secondary objectives are:

- To investigate the plasma PK of RO7020531, the main active metabolite RO7011785, and additional metabolites, including RO7018822 and RO7033805, in CHB patients.
- To investigate the PD markers of TLR7 activation, including cytokines and ISGs, following administration of RO7020531 to patients with CHB.

## **2.3 EXPLORATORY OBJECTIVES**

The exploratory objective for Part 2 (CHB patients) is:

- To investigate the antiviral effect of 6 weeks of treatment with RO7020531 in CHB patients.

## **3. STUDY DESIGN**

### **3.1 DESCRIPTION OF STUDY**

Part 1 will be a randomized, Sponsor-open, Investigator-blinded, subject-blinded, placebo-controlled, SAD and MAD study to evaluate the safety, tolerability, PK, and PD of RO7020531 and metabolites following oral administration to HVs. PK, PD, safety and tolerability data collected in the SAD portion of this study will be used to determine doses at which to initiate the MAD portion of the study.

Part 2 will commence when the data from SAD and MAD in HVs support the progression into the 6-week study in CHB patients after Internal Monitoring Committee (IMC) review as detailed in Section 3.1.2.2. This may occur before all MAD HV cohorts have been completed but not before data from at least the first MAD cohort have been reviewed. Part 2 will be a multiple-center, randomized, Sponsor-open, Investigator-blinded, patient-blinded, placebo-controlled study to investigate the safety, tolerability, PK and PD of treatment with RO7020531 for 6 weeks in patients with CHB infection.

#### **3.1.1 Overview of Study Design**

##### **3.1.1.1 Part 1: SAD in Healthy Volunteers**

HVs will be screened up to 28 days before randomization into the SAD portion of this study. For dose-escalation, volunteers will be sequentially randomized into one of approximately eight dose cohorts (Figure 1). The anticipated ascending dose scheme is 3 mg, 10 mg, 20 mg, 40 mg, 60 mg, 100 mg, 140 mg, and 170 mg. Additional cohorts may be added, and the doses chosen for evaluation in the SAD may be modified based on data from the previous cohorts. Initial dose-escalation will allow RO7011785 exposures in humans up to those documented at the NOAEL in the most sensitive species from the 13-week GLP toxicology studies (i.e., rats dosed 3 mg/kg QOD with an AUC of 0.4  $\mu\text{g} \cdot \text{h/mL}$ ). If adequate safety and tolerability are documented in humans, further dose-progression may be explored but not until a consensus agreement is reached between the Sponsor and the Investigator, and endorsed by the Independent Ethics Committee (IEC). Exposures higher than those associated with adverse effects in the monkey GLP toxicology studies (mean RO7011785 AUC  $\sim 2.8 \mu\text{g} \cdot \text{h/mL}$ ) are not to be explored in this study.

[figure not shown]
Due to anticipated variability in PD, cohort size will be fixed at eight subjects randomly assigned to RO7020531 and two subjects randomly assigned to placebo. Each cohort will include a minimum of two females, with at least one female receiving active drug. Safety and tolerability at each dose level will determine eligibility for dose-escalation. Measurement of PK and select PD markers will be made with each cohort and, upon availability, will be utilized along with safety data to determine an initial dose to initiate MAD in HVs. The SAD in HVs may continue until the maximum mean RO7011785 AUC of  $\sim 2.8 \mu\text{g} \cdot \text{h/mL}$  is reached based on the monkey GLP toxicology assessment or until dose-limiting toxicities are documented (see Section 3.1.2.1 for dose escalation criteria and stopping rules).

The MAD portion of this study in HVs may be initiated before the SAD portion is completed. Therefore, both the SAD and MAD portions of this study in HVs may run in parallel. All single and multiple doses in HVs will be administered in the fasted state. As an additional safety precaution in this EIH study, the subjects participating in each single dose cohort will be dosed according to a sentinel dosing design. Initially, two subjects will be dosed: one subject with RO7020531 and one subject with placebo. If the safety and tolerability results from the first 24 hours following dosing for the initial subjects are acceptable to the Investigator, the other subjects of each cohort may be dosed within shorter intervals.

In the SAD cohorts, volunteers will be asked to remain in the unit from Day -2 until Day 3 with dosing occurring on Day 1. After being discharged on Day 3, subjects will return for an outpatient clinic visit on Day 5 and for a follow-up outpatient visit on Day 8. All subjects will have a follow-up phone call 28 days after the study drug administration. Subjects will be asked to report any AEs that occur during this period.

**Figure 1 Study Design for Part 1: SAD and MAD in Healthy Volunteers\***

\*The figure shows anticipated doses for SAD cohorts 7 and 8.

### 3.1.1.2 Part 1: MAD in Healthy Volunteers

The trigger to start the first cohort in the MAD includes documentation of adequate safety and tolerability in the SAD. In addition, evidence in at least two subjects within a particular dose cohort exhibiting responses above placebo-defined baseline for select PD biomarkers should be demonstrated. These biomarkers include the protein and metabolite markers IFN- $\alpha$ , IL-12p40, IL-10, IP-10, TNF- $\alpha$ , IL-6, and neopterin and markers of transcriptional responses (ISG15, OAS-1, MX1 and TLR7). Once criteria have been reached to determine an initial dose for MAD, and there is evidence that the next higher dose is also well-tolerated as a single dose, then the MAD part will be initiated at the defined dose level. HVs will be screened up to 28 days before randomization into the MAD portion of this study. Only doses covered by the dose range evaluated in the SAD part will be used in the MAD part. The MAD study in HVs will consist of approximately 3 dose levels (Figure 1). The cohort size will be eight subjects randomly assigned to RO7020531 and two subjects randomly assigned to placebo. Each cohort will include a minimum of two female subjects, with at least one female on active drug.

Subjects randomized in the MAD study will be asked to remain in the unit from Day -2 until Day 14 with QOD dosing initiated on Day 1. In total, seven QOD doses will be administered with the last dose given on Day 13. Subjects will be discharged on Day 14.

After completing 7 QOD doses, each subject in the MAD cohorts will return for an outpatient follow-up visit 7 days after the last dose. All subjects will have a follow-up phone call 28 days after their last dose. Subjects will be asked to report any AEs that occur during this period.

Upon safety review (see Section 3.1.2), dose-escalation will proceed in the MAD part of this study until a maximal tolerated dose (MTD) or a mean RO7011785 AUC of  $\sim 2.8 \mu\text{g} \cdot \text{h/mL}$  is reached, or until it is determined that a suitable dose evaluation has been made by the Sponsor. The maximum dose investigated in MAD will not exceed doses evaluated in the SAD part.

Dose-escalation decisions in the MAD may utilize a Continual Reassessment Method (CRM) and may be modified accordingly. Information gained in the MAD part in HVs will be used to guide dose-selection for the study in CHB patients.

Based on the PK, PD and safety evaluation of the previous dose cohorts, additional cohorts of HVs may be enrolled at higher or lower dose levels, or at a dose level already tested.

### **3.1.1.3 Part 2: Chronic Hepatitis B Patients**

Part 2 will commence when the data from SAD and MAD in HVs support the progression into the 6-week study in CHB patients after IMC review as detailed in Section 3.1.2.2. This may occur before all MAD HV cohorts have been completed but not before data from at least the first MAD cohort have been reviewed. The decision to start the patient part and the recommendation for the starting dose level will be shared with investigators and the Ethics Committees/Institutional Review Boards before first dosing of a patient. Part 2 will consist of up to approximately four dose levels (Figure 2). Dose cohorts will randomize CHB patients who will be screened up to 28 days before randomization into the study. Patients in dose cohorts will receive study drug or placebo on a QOD schedule. Treatment duration in all cohorts will be 6 weeks with 6 weeks of follow-up. All doses will be given to patients in fasted state (at least 2 hours after a meal or 2 hours before the next meal).

*Cohorts 1, 2, and 3* will include eight patients receiving RO7020531 and two patients receiving placebo. Each cohort in Part 2 will include a minimum of two female patients, with at least one female patient receiving RO7020531. The dose level for the starting dose and subsequent doses in patients will be defined by the IMC based on a comprehensive review of available data in HV (all safety and PK, and select PD data), and will be lower than or equal to the dose that has been studied and has acceptable tolerability in the HV MAD part of the study.

In Cohorts 1, 2, and 3 all patients will continue taking commercially available NUC treatment (tenofovir, entecavir, adefovir, or telbivudine, either as single agents or in combination) orally once a day as per local label during study participation, including screening, the treatment period and follow-up.

The recruitment will start with 10 patients (8 receiving RO7020531 and 2 receiving placebo) randomized to Cohort 1. The first dose of oral RO7020531 or matching placebo will be given to each patient in the clinic on Day 1.

[figure not shown]
The recruitment will be suspended after the first 10 patients are randomized. When all 10 patients complete 6 weeks of treatment or discontinue study treatment prematurely, the assessment of the safety and tolerability of RO7020531 at the first dose level will be performed by the IMC. Based on the IMC safety review, progression of the study will be defined, including dose level for the next cohort (see Section 3.1.2.2). If the safety and tolerability are acceptable and a decision to open the next cohort is taken by the IMC and acknowledged by the active Investigators, the randomization will resume, and 10 patients will be randomized into Cohort 2.

The review of safety and tolerability in Cohort 2 will be performed in the same fashion by the IMC and will enable opening of optional Cohort 3.

The recommendation for the subsequent cohort dose level will be shared with the IEC/Institutional Review Boards (IRBs). Exploration of doses beyond the maximum proposed dose level will not occur until approval is received from the IEC/IRBs.

Both Cohorts 3 and 4 are optional and the study team may decide to conduct either one of these cohorts, or both. Cohort 4 will enroll CHB patients who are treatment naïve. The dose level for Cohort 4 has been pre-defined at the level of 150 mg RO7020531/placebo for 6 weeks on QOD schedule.

**Figure 2 Study Design for Part 2: Chronic Hepatitis B Patients**

### Follow-Up Period

After 6 weeks of study treatment, a follow-up period of 6 weeks will occur for patients in all treatment arms after receiving the last dose of RO7020531 or placebo.

### Optional In-Clinic Stay

To facilitate safety monitoring and the PK/PD assessment, patients will have an option to stay in the clinical unit for one night on Day 1 and/or Day 41. Patients will also have an option to not stay overnight in the clinical unit after the sampling on Day 1 or Day 41 and come to the site in the morning on Day 2 and/or Day 42 as per the SoA ([Appendix 1](#)) so that all required PK/PD samples are collected consistently and on time.

Additionally, there will be an optional overnight stay in the clinical unit on Day 1 at the Investigator's discretion for patients in Cohort 4 who develop flu-like symptoms/pyrexia during the first 12 hours post dose and do not respond to symptomatic treatment.

### 3.1.2 Dose-Escalation Decision Criteria and Stopping Rules

A Safety Review Meeting will be conducted by the Principal Investigator, the Medical Monitor, the Clinical Pharmacologist, and the Sponsor Clinical Team prior to each dose-escalation in the SAD and MAD portions in HVs (Part 1).

IMC meeting(s) will occur to undertake a comprehensive review of available data (all safety and PK, and select PD data) from the SAD and completed MAD HV cohort(s) to decide whether the data support progression into the 6-week study in CHB patients. The IMC will make recommendations for a starting dose, and subsequent doses for the Part 2 of the study. IMC dosing recommendations in Part 2 will be shared with and acknowledged by the active investigators, and shared with IEC/IRBs (see Section 3.1.3 for more details on IMC).

### **3.1.2.1 Part 1: SAD and MAD in Healthy Volunteers**

For all SAD and MAD cohorts, evaluable safety and tolerability data from a minimum of 8 subjects will be required in order to make the decision to escalate to the next dose. The maximum dose explored in HV will not exceed the exposure documented with adverse effects in the GLP toxicology studies.

The decision to escalate to the next dose level in the SAD cohorts will be based primarily on the safety and tolerability information through Day 4 (including AE, ECGs, vital signs, clinical laboratory test results) and, secondarily, on available PK through 24 hours post-dose and PD data at the previous dosage level. In addition, all available safety and PK data from the previous dose level(s) will be reviewed. The anticipated dose-escalation sequence for the SAD is 3 mg, 10 mg, 20 mg, 40 mg, 60 mg, 100 mg, 140 mg and 170 mg. If further cohorts are implemented, dose-escalations or dose modifications will be based on the documented safety and PK but not higher than double from the previous cohort.

The decision to escalate to the next dose level in the MAD cohorts will be based primarily on the safety and tolerability information (including AE, ECGs, vital signs, clinical laboratory test results) through Day 14 and, secondarily, on available PK data. In addition, all available safety and PK data from the previous dose level(s), including SAD cohorts, will be reviewed.

Depending on the evaluation of the safety and/or PK data, the same dose may be repeated; a lower dose may be administered; or intermediate dose-escalation steps other than those anticipated above may be used at the discretion of the Study Investigator and the Sponsor.

The recommendation for the subsequent cohort dose level will be shared with the IEC/IRB. Exploration of doses beyond the maximum proposed dose level will not occur until approval is received from the IEC/IRB.

Planned dose-escalation will be stopped if one of the following circumstances occurs in HVs treated with RO7020531, unless it is apparent that the occurrence is not related to the administration of study medication:

- Within a cohort, three or more HVs on active drug experience:
  - Severe and clinically significant (as defined by the Investigator) RO7020531-related AE of the same character, or
  - Clinically significant RO7020531-related laboratory abnormalities of the same character, or
  - Clinically significant RO7020531-related changes in vital signs or ECGs of the same character (e.g., confirmation of mean QTc 500 msec or 60 msec longer than the pre-dose baseline).
- Within two consecutive dose cohorts, four occurrences of any of the above conditions in HVs receiving active drug.
- Other findings (regardless of the incidence rates) that, at the joint discretion of the Sponsor and the Investigator, indicate dose-escalation should be halted.
- Dose-escalation will not proceed if it is predicted that higher doses of RO7020531 will not result in a further increase in RO7011785 plasma exposure; or if the mean systemic exposure (AUC) reaches the RO7011785 plasma levels found to be associated with adverse effects in the 13-week monkey GLP toxicology studies (i.e., mean AUC ~2.8 µg • h/mL).

If dose-escalation is stopped, lower doses could be investigated by mutual agreement between the Sponsor and the Investigator.

For stopping rules in an individual HV in the MAD study, see Section 4.7.1.1.

### **3.1.2.2 Part 2: Chronic Hepatitis B Patients**

The dose level for the starting dose and subsequent doses in patients will be defined based on a comprehensive review of available safety, PK and select PD data from the SAD and completed MAD cohort(s) in HVs by the IMC (see Section 3.1.3). The starting dose in patients will be lower than or equal to the dose that has been studied and has acceptable tolerability in the MAD part of the study, with evidence of PD effects in HVs (dose not higher than the MTD in HVs).

After the completion of dosing in Cohort 1 of Part 2, the decision on dose level for Cohort 2 will be taken by the IMC upon the review of data once all 10 patients have completed 6 weeks of treatment or have discontinued treatment prematurely (see Section 3.1.3). The IMC decision to open the next cohort will be acknowledged by the active investigators. Dose level selection after Cohort 1 may be guided by predictive models for safety as a function of dose. The dose levels for a subsequent cohort will not be higher than double compared to the previous cohort. The maximum dose in CHB patients will not exceed exposure documented with adverse effects in the monkey GLP toxicology studies.

The decision to open the optional Cohort 3 will be taken in the same fashion by the IMC upon the review of safety and tolerability in Cohort 2.

The dose for optional Cohort 4 has been predefined at the level of 150 mg QOD for 6 weeks. *For dose modifications in this cohort, see Section 4.4.2.3 and Section 5.2.1.*

The recommendation for the subsequent cohort dose level will be shared with the IEC/IRB. Exploration of doses beyond the maximum proposed dose level will not occur until approval is received from the IEC/IRB.

For stopping rules in patients, see Section 4.7.1.1.

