### **1.2.2 Previous Clinical Experience**

Study NP39305 is the first-in-human study of RO7020531.

*As of 01 May 2020, 110 healthy volunteers (HVs) in Part 1, and 30 CHB patients from Cohorts 1 to 3 and 9 CHB patients from Cohort 4 from Part 2 have been dosed in Study NP39305. The data from subjects in Part 1 and from patients in Cohort 1 in Part 2 were reviewed by IMC and shared with investigators. The treatment with RO7020531/placebo at all dose levels (Part 1: 3 mg, 10 mg, 20 mg, 40 mg, 60 mg, 100 mg, 140 mg, 170 mg; Part 2: 150 mg) was considered safe and had acceptable tolerability. An event of flu-like syndrome of moderate intensity was reported from a treatment naïve CHB patient from Part 2 Cohort 4 on Day 3. It was assessed as serious as it required or prolonged hospitalization and as related to the study drug by the investigator, and it resolved on Day 5. Adverse events (AEs) potentially related to pharmacodynamic (PD) effects expected with TLR7 agonist treatment were reported at dose levels >100 mg, including three HVs and seven CHB patients. They showed reversible signs and symptoms of immune activation after repeated dosing (e.g. flu-like symptoms) that resolved without sequelae. Apart from transient cytopenia observed in one of the patients, which improved during the dosing period, there have been no clinically significant changes in any other safety parameters, including laboratory assessments, vital signs and ECGs.*

RO7020531 showed a predictable PK profile. Similar to pharmacokinetics in single (SAD) and multiple (MAD) ascending dose cohorts from HVs, the active TLR7 agonist,

RO7011785, appeared rapidly in plasma following 150 and 170 mg dosing of CHB patients on Day 1 with a  $T_{max}$  ranging from 1.0 to 2.0 hr and was eliminated relatively quickly from plasma with a mean terminal half-life of ~4 hours.

Individual  $C_{max}$  and  $AUC_{0-inf}$  of RO7011785 following 150 and 170 mg of RO7020531 in CHB patients appears to be within the range of prediction from SAD/MAD healthy volunteer data. However, the mean RO7011785  $AUC_{0-inf}$  of 2814 ng\*hr/mL on Day 1 is slightly higher (~15%) than the expected value, with greater inter-subject variability, and numerically comparable to mean exposure associated with the monkey lowest observed adverse effect level (LOAEL) (2780 ng\*hr/mL).

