*After Study NP39305 had been started, Study YP39553 was initiated. YP39553 was a Phase 1 bridging study to evaluate the PK, PD, and safety/tolerability of RO7020531/placebo in Chinese HV in 4 SAD cohorts (40, 100, 140, and 170 mg) and three MAD cohorts (100 mg, 150 mg and 150 mg). This study has been completed. A total of 70 Chinese HV were dosed in study YP39553. The treatment with RO7020531/placebo was safe with acceptable tolerability when administered orally as a single dose of up to 170 mg and as multiple doses up to 100 mg QOD. A total of nine subjects (8 subjects from the MAD 150 mg cohorts and one subject from the SAD 170 mg cohort) experienced pyrexia/flu-like symptoms after the first, second, or the third dose of the study drug. Of these nine subjects with flu-like symptoms, six had AEs of moderate intensity and three had AEs of mild intensity. In all these subjects, there were no clinically significant changes in vital signs (except pyrexia) and ECGs. Unscheduled laboratory tests performed at the time of pyrexia (5.5 to 12 hours post dose) revealed that seven subjects from MAD 150 mg cohorts had Grade 1 to 4 lymphopenia and the Principal Investigator decided to discontinue further drug administration in these seven subjects. Lymphocyte counts returned to normal levels within 24 to 48 hours in all subjects. One subject from the 150 mg MAD dose cohort decided to withdraw from the study after the fifth dose.*

Following single oral doses of RO7020531, the PK of the active metabolite RO7011785 is linear and mean  $AUC_{0-inf}$  increased in a dose proportional manner from 40 mg to 170 mg. No PK accumulation was observed following dosing QOD dosing regimen over the 2-week period. Both single and multiple doses of RO7020531 resulted in dose-dependent increases in TLR7 response marker at the dose of 100 mg or above, and the flu-like symptoms are associated with higher PD response.

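### Does the mean AUC of 2814 ng·h/mL reported in hepatitis B patients contradict the protocol's exposure limit of about 2.8 µg·h/mL?

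*Combined protocol and SAP*

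**What the plan says.** The limit appears in several places. Section 3.1.2.2, on dose levels in Part 2, says: "The maximum dose in CHB patients will not exceed exposure documented with adverse effects in the monkey GLP toxicology studies". Section 3.1.1.1 rules out for the study "Exposures higher than those associated with adverse effects in the monkey GLP toxicology studies", and puts that level at a mean RO7011785 AUC of about 2.8 µg·h/mL. Section 3.2.1 repeats this and adds that doses are to be designed to give exposures below those linked to adverse effects in animals.

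The patient data are in Section 1.2.2. The active metabolite "appeared rapidly in plasma following 150 and 170 mg dosing of CHB patients on Day 1". Individual values at these two doses are said "to be within the range of prediction from SAD/MAD healthy volunteer data". The text then gives a mean AUC0-inf "of 2814 ng\*hr/mL on Day 1 is slightly higher (~15%) than the expected value, with greater inter-subject variability", which it calls "numerically comparable to mean exposure associated with the monkey lowest observed adverse effect level (LOAEL) (2780 ng\*hr/mL". It gives no number of patients, SD or CV, and ties the mean to neither dose.

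By 1 May 2020, "30 CHB patients from Cohorts 1 to 3 and 9 CHB patients from Cohort 4" had been dosed. The Cohort 4 dose is predefined at 150 mg every other day, with reduced regimens allowed.

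**The concern.** Read literally, 2814 is greater than 2780, so a protocol that promises not to go above the monkey adverse-effect exposure appears to report a patient mean above it. The missing label makes this harder to dismiss. If 2814 is a 150 mg mean or a pool, the 170 mg mean would be expected to lie higher still. The text also says the mean ran above expectation with more spread between patients, and no visible sentence says how the figure was judged against the limit. At stake is whether the stated safety ceiling for patients still describes the doses given, and whether an ethics committee could tell.

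**Working it through.** **Inputs.** Observed mean 2814 and monkey mean 2780 ng·h/mL (Section 1.2.2). Limit of about 2.8 µg·h/mL (Sections 3.1.1.1 and 3.2.1). Eight active patients per cohort in Cohorts 1–3 (Section 3.1.1.3). Cohort 1 at 150 mg (Section 3.2.2.2). The 2814 cannot be recomputed, because no individual values, n or SD are given.

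**1. Size of the gap.** 2814 − 2780 = 34 ng·h/mL, and 2814/2780 = 1.012, so +1.2%. In the limit's units the two figures are 2.814 and 2.780 µg·h/mL, and both are 2.8 to one decimal.

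**2. Sampling error.** The CV and n are assumptions: CV 20–50%, n 8–24. The standard error as a share of the mean is CV/√n, from 0.20/√24 = 4.1% to 0.50/√8 = 17.7%. The gap is 34/(2814 × 0.041) = 0.30 down to 34/(2814 × 0.177) = 0.07 standard errors. The 95% t-interval for the mean runs from 2576–3052 at the narrowest to 1638–3990 at the widest. All such intervals contain 2780.

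**3. What the missing label could hide.** Assume AUC proportional to dose. For n₁ patients at 150 mg and n₂ at 170 mg, k = 2814(n₁ + n₂)/(150n₁ + 170n₂), and the two means are 150k and 170k.

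| Reading of 2814 | 150 mg mean (vs 2780) | 170 mg mean (vs 2780) |
|---|---|---|
| All 170 mg | 2483 (−10.7%) | 2814 (+1.2%) |
| Pool 8:16 | 2584 (−7.0%) | 2929 (+5.4%) |
| Pool 8:8 | 2638 (−5.1%) | 2990 (+7.5%) |
| Pool 16:8 | 2694 (−3.1%) | 3053 (+9.8%) |
| All 150 mg | 2814 (+1.2%) | 3189 (+14.7%) |

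The pool splits are assumptions, since the doses of Cohorts 2 and 3 are not given separately. Proportionality is reported only for Chinese healthy volunteers in another study, where AUC "increased in a dose proportional manner from 40 mg to 170 mg".

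**4. How firm the 170 mg column is.** It needs the observed 170 mg mean to be at least the observed 150 mg mean. Suppose the true means are proportional to dose. The chance that the observed means come out reversed is Φ(−20/(CV·√(150²/n₁ + 170²/n₂))). At CV 20% and 8:16 this is Φ(−20/13.6) = Φ(−1.47) = 7%. At CV 50% and 8:8 it is Φ(−20/40.1) = Φ(−0.50) = 31%. The ordering is likely but not assured.

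**5. What was expected when doses were chosen.** The text puts 2814 about 15% above expectation, so the expected mean was about 2814/1.15 = 2447, which is 12.0% below 2780. Even if 2814 and its expected value both belong to 150 mg, the expected 170 mg mean is 2447 × 170/150 = 2773, just below 2780. With the 15% read as 14.5–15.5%, that becomes 2761–2785.

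**6. Who is still to be dosed.** Cohorts 1–3 plan 10 patients each, and 3 × 10 = 30 had been dosed. Cohort 4 takes up to 15, with 9 dosed, so at most 15 − 9 = 6 remain. Some of those are on placebo, given the 4:1 allocation. Replacements for non-safety withdrawals are ignored.

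**The case for a change.** The strongest case is that imprecision cuts both ways. If 2814 does not prove an exceedance, it does not prove compliance either. At 170 mg the point estimate is 2814 or more on every reading in which the two means keep their expected order, and under proportionality it stays below 2850, the upper edge of what rounds to 2.8, in only one of five readings. Review of PK for every patient (Section 4.6.2.2), an unblinded Sponsor team (Section 4.3) and Clinical Pharmacology membership of the Internal Monitoring Committee (Section 3.1.3) are processes; they do not record how this figure was judged. Labelling the mean by dose would cost almost nothing.

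Part of this stands. Section 1.2.2 would be clearer with the dose, n and CV behind 2814, and the 170 mg question cannot be closed from the visible text. But the comparison is not hidden: the protocol sets 2814 beside 2780 in the same sentence. Sections 3.1.2.2 and 3.2.1 look forward, to the design and choice of doses, so a later observed mean 1.2% above 2780 does not contradict them. What a committee could tell cannot be judged from this copy either. Parts of Sections 1.3.2 and 5.2.1 are blacked out, the Investigator's Brochure is not included, and dose recommendations were to be shared with the ethics committees.

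**Conclusion.** No change to the plan follows. The documents show a mean 34 ng·h/mL (1.2%) above 2780, equal to the limit at the one-decimal precision in which the limit is written, and 0.07 to 0.30 standard errors from it under the assumed CV and n. That is a missing label on a background figure, not a demonstrated contradiction.

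The gap is one that analysts will fill. Sections 3.3.2.1 and 6.8 already call for mean, SD and CV of the PK parameters by dose cohort or treatment arm, and those tables will show which dose the 2814 belongs to. Adding the label to Section 1.2.2 would alter no dose, analysis or conclusion: the planned 30 patients in Cohorts 1–3 had been dosed, and the remaining Cohort 4 patients, at most 6 before any replacements, are planned at 150 mg or a reduced regimen. At 150 mg the point estimate is below 2780 in four of the five readings.

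This rests on the visible text, on assumed CVs and pool splits, and on proportionality taken from another study's healthy volunteers. If the by-dose summaries put a patient mean clearly above the limit, Section 1.2.2 and the limit statements would then have to be reconciled. No view is taken here on which dose or limit is right.
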